#### 9.1.2 $^{89}\text{Zr}$ -df-IAB2M PET/CT imaging

##### 9.1.2.1 Method of Assessment

PET/CT will be read twice by a nuclear medicine physician. For the first interpretation, the physician will be blinded from clinical history, biopsy results and conventional

imaging modalities. After the initial reading, the nuclear medicine physician will be provided with both the TRUS biopsy results and previously read scans for the repeat PET/CT reading. During each interpretation, the physician will record all abnormal, suspicious areas with higher uptake than adjacent or contralateral background. Each abnormal area will be recorded on a map of the prostate along with maximum standardized uptake value ( $SUV_{max}$ ) and mean standardized uptake value ( $SUV_{mean}$ ).

Subsequently, the accumulation of  $^{89}Zr$ -df-IAB2M will be compared to areas of known PCa foci on histopathology and mpMRI, as described in Section 13. After completion of the histopathology, the PET/CT findings will be compared to histopathology to perform a lesion by lesion analysis with histopathology serving as the reference gold standard. This analysis will primarily include tumors  $\geq 0.5 \text{ cm}^3$  on histopathology, with a secondary assessment of any lesions  $<0.5 \text{ cm}^3$ . Similarly, areas of increased uptake identified on IAB2M, which had been read as suspicious for cancer will be compared to histopathology to determine the underlying pathology (e.g., inflammation, benign prostatic hyperplasia).

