### Primary endpoints

The primary endpoint of this study is the proportion of subjects with PSMA-positive (identified by H&E staining and immunohistochemistry) "dominant" PC lesion(s) greater than 5mm in diameter, whose lesion(s) have been successfully identified by  $^{89}\text{Zr}$ -df-IAB2M imaging. Because this is an exploratory pilot study, no formal sample size/power calculation is required. However, with a sample size of 20 patients in the study, a two-sided 95% confidence interval for the proportion of patients successfully imaged by  $^{89}\text{Zr}$ -df-IAB2M can be constructed to be within  $\pm 19.0\%$  of the observed proportion of patients with successful imaging by  $^{89}\text{Zr}$ -df-IAB2M. This calculation assumes an  $^{89}\text{Zr}$ -df-IAB2M imaging-success proportion of 75%. All estimates from the study will serve as preliminary data (i.e., hypothesis-generating) for future studies.

- Descriptive statistics will be calculated for the study cohort:
  - Median and inter-quartile range or mean and standard deviation for age, biopsy Gleason score (1o, 2o, Total), number of cores on biopsy, number of positive cores on biopsy, PSA, number of lesions on prostatectomy pathology (RP pathology), lesion size on RP pathology, Gleason score (1o, 2o, and total) on RP pathology.
- Lesion-based analysis:

- SUVmax measurements of Zr-df-IAB2M PET/CT images obtained in tumor and non-tumor regions will be compared. To account for inpatient correlation of multiple lesions, a linear mixed-effects model with a random intercept will be used to estimate and compare the mean SUVmax values in different regions.  $P < 0.05$  will be indicative of a significant difference as described by Turkbey B, et al.
- Positive and negative predictive values will be estimated by using generalized estimating equations (GEE) modeling, with logit link function and a working independence correlation structure. Robust variance estimation and the delta method will be used to calculate standard errors of the positive and negative predictive values. The Wald test with robust variance estimates will be used for statistical inference. Subgroup analyses will be performed for high, moderate, and low risk disease (see secondary endpoints).

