### Secondary endpoints

- To determine the ability of *in vivo* Zr-df-IAb2M PET/CT to correlate with pathological features (i.e. Gleason pattern, diameter and PSMA-positivity):
  - The Wilcoxon rank sum test will be used to compare lesions that were and were not identified on *in vivo* PET with respect to lesion size, immunohistochemical PSMA staining, and Gleason score (demonstrated by histopathology). This lesion based analysis will be performed in a similar fashion as described above.
- To compare the *in vivo* Zr-df-IAb2M PET/CT and Ga-PSMA-HBED-CC PET/CT to *in vivo* mpMRI:
  - The diagnostic accuracy of Zr-df-IAB2M PET/CT and Ga-PSMA-HBED-CC PET/CT imaging in patients with prostate cancer will be compared with that of mpMRI imaging by using sector-based analysis, as described by Turkbey B et al. The estimates of patient-specific sensitivity and specificity will be defined as the proportion of true-positive sectors and the proportion of true-negative sectors in each patient. Overall sensitivity and specificity will then be estimated by calculating the mean (and standard error) of these individual-

specific estimates across patients. Differences in sensitivity and specificity between modalities will then be evaluated by the Wilcoxon signed-rank test.

- To determine the sensitivity, specificity, PPV, NPV of IAB2M to detect all pathologically identified PCa lesions that do not meet criteria for clinical significance (defined as:  $< 0.5 \text{ cm}^3$  with Gleason pattern  $< 4$ ):
  - As above, but for lesions considered not to be clinically significant.
- To correlate IAB2M positivity (SUV) and lesion size:
  - The Spearman-rank correlation coefficient will be used to evaluate the association between SUV and size of the lesion (procedure for size measurements are defined in Section 9.1.3).
- To correlate IAB2M positivity (SUV) and Gleason pattern (3, 4 and 5):
  - The Spearman-rank correlation coefficient will be used to evaluate the association between correlate SUV and the histopathologically defined Gleason pattern. The Wilcoxon rank-sum test will also be used to compare  $\text{SUV}_{\text{max}}$  measurements between lesions with low Gleason score (3+4 or lower) and high Gleason score (4+3 or higher).
- To correlate IAB2M positivity (SUV) and PSA:

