  - The Spearman-rank correlation coefficient will be used to evaluate the association between SUV and serum PSA levels obtained during screening.
- To determine the ability of *in vivo*  $^{89}\text{Zr}$ -df-IAB2M PET/CT to identify extra-prostatic extension:
  - The Wilcoxon rank-sum test will be used to compare  $\text{SUV}_{\text{max}}$  measurements of IAB2M-positive extra-prostatic sites between lesions with and without histopathologically confirmed extra-prostatic extension.
- To determine the ability of *in vivo*  $^{89}\text{Zr}$ -df-IAB2M PET/CT to identify occult lymph node involvement:

- The Wilcoxon rank-sum test will be used to compare  $SUV_{max}$  measurements of IAb2M-positive lymph nodes between patients with and without histopathologically confirmed lymph node involvement.
- To further evaluate the safety of  $^{89}Zr$ -DF-IAB2M PET/CT and  $^{68}Ga$ -PSMA-HBED-CC imaging.
  - See section on Risks

Additionally, we will assess whether there is improved sensitivity in detecting localized PCa by combining imaging results. This assessment will be done by estimating the PPV with different combinations of imaging modalities. The incremental effect of an additional imaging modality on PPV will be tested with the Wald test, as described by Turkbey B, et al.

All p-values will be two-sided with statistical significance evaluated at the 0.05 alpha level. All analyses will be performed in SAS Version 9.4 (SAS Institute, Inc., Cary, NC) and Stata Version 13.0 (StataCorp, College Station, TX).

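### The combined-modality analysis asks about sensitivity but estimates and tests only PPV, which counts no missed disease

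*Combined protocol and SAP*

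**What the plan says.** Near the end of section 12.1, Secondary endpoints, the plan adds an analysis of combined imaging. It will "assess whether there is improved sensitivity in detecting localized PCa by combining imaging results. This assessment will be done by estimating the PPV" for the various combinations, and "The incremental effect of an additional imaging modality on PPV will be tested with the Wald test", following the cited 18F-FACBC PET/CT study (reference 59). That paragraph names no other accuracy measure and gives no combination rule, model or unit of analysis.

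Other parts of the plan that bear on the point:

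- **Section 12.1, Primary endpoints, lesion-based analysis:** "Positive and negative predictive values will be estimated by using generalized estimating equations (GEE) modeling", with a logit link, working independence and robust variance. An ROC analysis of SUV follows.
- **Section 12.1, Secondary endpoints, comparison with mpMRI:** sector-based sensitivity and specificity are "defined as the proportion of true-positive sectors and the proportion of true-negative sectors in each patient", averaged over patients and compared by signed-rank test. Only single modalities are covered. A further endpoint gives sensitivity of IAB2M alone for lesions that are not clinically significant.
- **Section 9.1.2.1:** the PET reader records "areas with higher uptake than adjacent or contralateral background" at two reads. At the first, "the physician will be blinded from clinical history, biopsy results and conventional" imaging; for the second the reader is "provided with both the TRUS biopsy results and previously read scans for the repeat PET/CT reading".
- **Section 9.1.1.1:** the mpMRI reader has the biopsy results.
- **Extension and nodes:** the extension objective is tested by a rank-sum comparison of SUVmax "measurements of IAB2M-positive extra-prostatic sites between lesions with and without histopathologically confirmed extra-prostatic extension". The node objective is tested in the same way among IAB2M-positive nodes.

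**The concern.** Sensitivity is the share of diseased sectors that are called. PPV is the share of called sectors that are diseased. Adding a modality changes both, and which way each moves depends on how the two readings are joined. A significant PPV gain could therefore be reported as improved sensitivity when more cancer was being missed. A real gain in sensitivity could also be overlooked because PPV fell. The plan says its estimates will feed future studies, so the wrong label could be carried forward.

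A smaller and separate gap concerns extra-prostatic extension and lymph nodes. The objectives in section 1.2 are about identifying them, but the only test is among sites or nodes that PET already called. Confirmed disease that PET missed never enters.

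**Working it through.** **The plan's own figure.** The only precision figure is the ±19.0% in sections 12.1 and 12.2: 1.96 × √(0.75 × 0.25 / 20) = 0.190. It reproduces and is not in dispute. The documents give no figure for the combination analysis, so every accuracy and prevalence input below is an assumption.

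**Step 1: definitions.** Sensitivity = TP/(TP+FN); PPV = TP/(TP+FP). With TP = 30 and FP = 10, PPV is 0.75 whether FN is 10 (sensitivity 30/40 = 0.75) or 60 (sensitivity 30/90 = 0.33).

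**Step 2: direction.** The sectors called under an either-positive rule include all those called by each component, so FN cannot rise and sensitivity cannot fall. The sectors called under a both-positive rule are a subset of each component's, so sensitivity cannot rise. PPV is not bound in either case.

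**Step 3: illustration.** Assume 70% sensitivity and 90% specificity for each modality, 25% of sectors positive, and independence given true status. PPV = se × prev / [se × prev + (1 − sp)(1 − prev)].

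| Reading | Sensitivity | Specificity | PPV |
|---|---|---|---|
| Single | 0.70 | 0.90 | 0.175/0.250 = 0.70 |
| Either-positive | 1 − 0.3² = 0.91 | 0.9² = 0.81 | 0.2275/0.3700 = 0.61 |
| Both-positive | 0.7² = 0.49 | 1 − 0.1² = 0.99 | 0.1225/0.1300 = 0.94 |

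With half the maximum covariance between the modalities, both-positive sensitivity is 0.49 + 0.5 × 0.21 = 0.595 with PPV 0.78. Either-positive sensitivity is 0.805 with PPV 0.65. The contrast shrinks but keeps its direction.

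**Step 4: a case where both rise.** Start from a modality with 70% sensitivity and 80% specificity, PPV 0.175/0.325 = 0.54. Add one with 70% and 99% under the either-positive rule. Sensitivity rises to 0.91, and PPV becomes 0.2275/(0.2275 + 0.208 × 0.75) = 0.59.

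**Step 5: how often the test would mislead.** The simulation assumes a sector-level logit GEE with working independence and robust variance by patient, the Step 3 accuracies, patient prevalence drawn from Beta(2.5, 7.5), 20 patients and 4,000 runs per cell. Significance is two-sided p < 0.05.

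| Sectors per patient | Dependence | Both-positive: significant PPV gain | Either-positive: significant PPV drop |
|---|---|---|---|
| 12 | independent | 81% | 60% |
| 12 | half covariance | 51% | 36% |
| 24 | independent | 97% | 89% |
| 24 | half covariance | 87% | 67% |

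In the first row a further 16% of both-positive runs could not be estimated because PPV was 100%. Sensitivity changes by about 21 points (independent) or 10.5 points (half covariance): down under both-positive, up under either-positive. I give no rates for 10 patients, because about 39% (12 sectors) and 15% (24 sectors) of the independent runs were not estimable.

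**Step 6: is sensitivity for combinations planned elsewhere?** No. The GEE analysis gives PPV and NPV, the ROC analysis concerns SUV, and the sector analysis takes one modality at a time.

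**Step 7: a p-value for sensitivity would not help.** When a combination is compared with one of its components, all changes go one way. The exact signed-rank p-value is then 2/2ⁿ for n patients who change, so six changers give 2/64 = 0.031 whatever the merit of the combination.

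**The case against.** The strongest reply is that this is one misplaced word. Estimating PPV and Wald-testing PPV agree with each other and with the PPV and NPV methods planned for lesions. Combined imaging is not an objective in section 1.2, and the study is described as exploratory. That stands as an argument about weight. It does not remove the mismatch, because the stated question is still one that the analysis cannot answer.

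A second reply is that the analysis is deferred to reference 59, which may define the combination rule. That also stands: it cannot be said that no rule exists, only that these documents do not state one. But no rule puts false negatives into PPV.

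A third reply is that the simulation is not the sponsor's test. This is correct. The combination paragraph names no model or unit, and the GEE text sits under the lesion-based analysis, so the simulated rates belong to an assumed sector-level version.

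A reader might infer that PPV always moves against sensitivity. Step 4 shows that it does not. A reader might also infer that the plan neglects sensitivity altogether. It does not: section 12.1 plans it for single modalities. Nor is the extension and node analysis a contradiction of the same kind. It is an omission, and it adds no weight to the main point.

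**Conclusion.** The point holds as a should-fix mismatch between question and measure. The combination analysis is worded as a test of sensitivity, yet it estimates and tests a quantity that missed disease does not enter. That conclusion needs no assumed number. The size does: on the Step 3 inputs sensitivity moves by about 10 to 21 points, and with 20 patients the assumed test gives a significant PPV change in the opposite direction in 36% to 97% of trials, depending on rule, sector count and correlation.

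The documents do not support extending this to the primary endpoint, the sample size or the interim look, none of which uses the combination analysis. The extension and node gap is minor: those objectives would be reported with no count of missed disease.

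**What to change.** In the combination paragraph of section 12.1:

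1. State the rule or rules: either-positive, both-positive, or the one taken from reference 59.
2. Estimate per-patient sector sensitivity and specificity for each combination and each single modality, using the method already planned for the mpMRI comparison. Name the denominators (histology-positive and histology-negative sectors). Restrict the analysis to patients who had every scan being combined, and report that number.
3. Use the blinded first PET read. State that the mpMRI reader has the biopsy results, so any gain from adding mpMRI may partly reflect biopsy knowledge.
4. Report the changes in sensitivity and specificity together, with approximate 95% intervals clustered by patient. Give no p-value where the rule fixes the direction, and do not read an interval that excludes zero as evidence there.
5. Keep PPV as an additional result that is not called sensitivity.

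If PPV is the intended measure, replacing the word sensitivity is enough, provided that no sensitivity conclusion is drawn.

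For extension and nodes, report descriptively how many histologically confirmed extensions and involved nodes were and were not called on PET, with exact intervals. Match by site where section 9.1.4.1 records location, and limit nodes to patients who had a dissection. Do not describe the SUVmax comparison as ability to identify disease.

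**Cost:** some added analysis, a recorded sector call for 68Ga (section 9.1.3 describes acquisition only) and a recorded extra-prostatic PET call (section 9.1.2.1 names only a prostate map). mpMRI is conditional in section 10, footnote e, so some patients may drop out of combinations. Precision will be poor. In simulation, a patient-level bootstrap interval for the both-positive change in sensitivity was 13 to 24 points wide with 20 patients and covered 89% to 92%, hence the label approximate. For small counts, 5/6 gives 36% to 100% and 2/4 gives 7% to 93%.

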## 12.2 Sample Size/Accrual Rate

The sample size for this study will be 20 patients. We anticipate an accrual rate of at least two patients per month. With a sample size of 20 patients in the study, a two-sided 95% confidence interval for the proportion of patients successfully imaged by  $^{89}Zr$ -df-IAB2M can be constructed to be within  $\pm 19.0\%$  of the observed proportion of patients with successful imaging by  $^{89}Zr$ -df-IAB2M. This calculation assumes an  $^{89}Zr$ -df-IAB2M imaging-success proportion of 75%. All estimates from the study will serve as preliminary data (i.e., hypothesis-generating) for future studies.”

## 12.3 Stratification Factors

No stratification factors. However, an interim analysis and efficacy determination based on the primary endpoint will be performed after the first 10 patients have completed Visit 4 and subsequent histopathological analysis has been performed on the prostate specimen.

## APPENDIX A

### Performance Status Criteria

ECOG Performance Status Scale		Karnofsky Performance Scale	
Grade	Descriptions	Percent	Description
0	Normal activity. Fully active, able to carry on all pre-disease performance without restriction.	100	Normal, no complaints, no evidence of disease.
		90	Able to carry on normal activity; minor signs or symptoms of disease.
1	Symptoms, but ambulatory. Restricted in physically strenuous activity, but ambulatory and able to carry out work of a light or sedentary nature (e.g., light housework, office work).	80	Normal activity with effort; some signs or symptoms of disease.
		70	Cares for self, unable to carry on normal activity or to do active work.
2	In bed <50% of the time. Ambulatory and capable of all self-care, but unable to carry out any work activities. Up and about more than 50% of waking hours.	60	Requires occasional assistance, but is able to care for most of his/her needs.
		50	Requires considerable assistance and frequent medical care.
3	In bed >50% of the time. Capable of only limited self-care, confined to bed or chair more than 50% of waking hours.	40	Disabled, requires special care and assistance.
		30	Severely disabled, hospitalization indicated. Death not imminent.
4	100% bedridden. Completely disabled. Cannot carry on any self-care. Totally confined to bed or chair.	20	Very sick, hospitalization indicated. Death not imminent.
		10	Moribund, fatal processes progressing rapidly.
5	Dead.	0	Dead.

**APPENDIX B**

**WCMC IRB SAE Reporting Forms**

[http://researchintegrity.weill.cornell.edu/institutional\\_review\\_board/irb\\_adv.html](http://researchintegrity.weill.cornell.edu/institutional_review_board/irb_adv.html)
